9.4.1 KCCQ

KCCQ, is a widely used 23-item, disease-specific health status measure intended for the assessment of heart failure patients' perspectives of how their disease impacts their lives (24). It is a self-administered PRO instrument and requires, on average, 4–6 minutes to complete. Patients are asked to recall how their heart failure impacted their life over a 2-week recall period. Response options are on a 5- to 7-point Likert-type scale with varying response options depending on the question.

The KCCQ measures the impact of patients' heart failure, or its treatment, on 6 domains; Physical Limitation, Symptom (with subscores for frequency and burden), Quality of Life, Social Limitations, Symptom Stability and Self-Efficacy. Scores are calculated by summing domain responses and then transforming scores to a 0-100 unit scale with higher scores indicating better health status. In addition, the KCCQ includes 2 summary scores, CSS an equally weighted composite of Physical limitation and Total Symptom domain scores, and OSS which additionally combines the social limitation and quality of life domain scores to the CSS (Table 9–2).

Clinical Study Protocol
No. BAY 1021189 / 19334

22 FEB 2018

Version no. 1.0

Page: 49 of 81

Table 9–2: KCCQ Domains and Summary Scores

KCCQ Domain	Description ^a
Efficacy Domains	
Physical Limitation ^b	The limitations patients' experience, due to their heart failure symptoms, in performing routine activities. Activities are common, gender-neutral, and generalizable across cultures, while also capturing a range of exertional requirements.
Symptom ^c	The frequency and burden of clinical symptoms in heart failure, including fatigue, shortness of breath, paroxysmal nocturnal dyspnea and patients' edema/swelling. An overall symptom score is generally used in analyses; subscale scores for both frequency and severity are also available.
Quality of Life	Designed to reflect patients' assessment of their quality of life, given the current status of their heart failure.
Social Limitation	The extent to which heart failure symptoms impair patients' ability to interact in a number of gender-neutral social activities.
Non-Efficacy Domains	
Symptom Stability	Measures recent changes in patients' symptoms; their shortness of breath, fatigue or swelling. It compares patients frequency of heart failure symptoms at the time of completing the KCCQ with their frequency 2 weeks ago. This domain is not included in the summary scores.
Self-efficacy	Patient perceptions of how to prevent heart failure exacerbations and manage complications when they arise. This scale is not included in the summary scores.
Summary Scores	
Clinical Summary	Includes total symptom and physical function scores to correspond with NYHA Classification.
Overall Summary	Includes the total symptom, physical function, social limitations and quality of life scores

a Descriptions of KCCQ Domain and summary scores are taken from the FDA document Medical Device Development Tool (MDDT) Qualification Decision Summary for Kansas City Cardiomyopathy Questionnaire (KCCQ) (27) with minor editing for brevity.

b 'Physical Function' also used as domain name.

c Often reported as 'Total Symptom Score'.

KCCQ Physical Limitation Score (PLS) has been selected as the primary endpoint in the trial as it is a direct measure of the hypothesized treatment effect; improvement in functional capacity in activities of daily life limited by the symptoms of heart failure. PLS measures the limitations patients' experience, due to their heart failure symptoms (shortness of breath or fatigue), in performing routine activities of daily life (Table 9–3). The PLS is calculated through an algorithm applying equal weighting to each of the items and a transformation to a 0–100 scale. Other KCCQ domains including Symptom (frequency, burden and overall), Quality of life and Social limitation together with the Clinical and Overall summary scores will be reported as exploratory endpoints. The KCCQ domains of Symptom Stability and Self-efficacy will be reported but will not be considered measures of treatment efficacy.

Table 9-3: KCCQ - Physical Limitation domain item wording

Item activity description ^a	Response scale (for all items)
(a) Dressing his/herself	1. Extremely limited
(b) Showering / bathing	2. Quite a bit limited
(c) Walking 1 block on level ground	3. Moderately limited
(d) Doing yard work, housework or carrying groceries	4. Slightly limited
(e) climbing a flight of stairs without stopping	5. Not at all limited
(f) Hurrying or jogging (as if to catch a bus)	6. Limited for other reasons or did not do the activity

a The patient is asked to indicate how much he/she is limited by heart failure (shortness of breath or fatigue) in his/her ability to do the described activities over the past 2 weeks.

9.4.2 EQ-5D-5L

The EQ-5D-5L is a self-administered generic measure of health-related quality of life which includes five dimensions: mobility, self-care, usual activities, pain/discomfort, and anxiety/depression. Patients provide a rating for each question on a five-level Likert scale: having no problems, having slight problems, having moderate problems, having severe problems and being unable to do/having extreme problems. In addition, patients are asked to self-rate their own health today on a vertical 0-100 unit visual analogue scale (VAS), with 0 corresponding to "the worst health you can imagine", and 100 corresponding to "the best health you can imagine".

9.4.3 Patient Global Impression of Change (PGIC), and Severity (PGIS)

PGIC contains one question (1a) asking the patient to assess the degree of change in physical limitation due to heart failure compared to the start of the treatment using the following response options: "much better", "better", "a little better", "the same", "a little worse", "worse", or "much worse". A subsequent question (1b) then asks the patient to indicate whether he/she feels the degree of change reported is important or not (yes/no).

PGIS contains one question asking the patient to assess the current severity of their physical limitations due to heart failure using the following response options: "No limitations", "Mild", "Moderate", "Severe", or "Very severe"

It is anticipated to take approximately 2-3 minutes to complete both the PGIC and PGIS questions. Data from these questions will be used to provide anchors for estimating minimally important differences in physical limitations in heart failure.

9.4.4 Fried frailty score

The Fried frailty phenotype defines 5 key domains for frailty (28) weakness, low energy, slowed walking speed, decreased physical activity, and weight loss. It quickly garnered attention in the CV community (29). Fried's frailty score is on the basis of an integrated biological perspective, without focus on a single aspect of decline but the overall context of homeostasis. The Fried score differentiates frailty from multimorbidity and disability,

articulating that frailty predisposed to the other conditions, but frailty was a distinct biologic syndrome (30).

The questions patterned from the Fried Frailty score domains are assessed at baseline and at 24 weeks (31). The questions address five domains of the frailty phenotype: (a) shrinking (weight loss of ≥ 10 pounds in the prior year); (b) weakness (decreased or weakened grip strength); (c) exhaustion (fatigue or declining endurance); (d) slowness (slower walking pace); and (e) low activity (decline in physical activity). The 5 questions are as follows:

Questions at baseline:

Within the last 12 months has the patient experienced any of the following?

- Unintentional weight loss (≥ 5 kg/10 lbs).
- Developed decreased grip strength.
- Developed increasing fatigue/lethargy or declining endurance.
- Walks a distance of 5 m/15 feet at a slower pace.
- Decline in typical activity level.

Questions at 24 weeks:

Within the last 6 months has the patient experienced any of the following?

- Unintentional weight loss (≥ 5 kg/10 lbs).
- Developed decreased grip strength.
- Developed increasing fatigue/lethargy or declining endurance.
- Walks a distance of 5 m/15 feet at a slower pace.
- Decline in typical activity level.

9.4.5 Assessment of NYHA class

NYHA class will be assessed according to the classification below:

- Class I: No limitation of physical activity
- Class II: Slight limitation of physical activity in which ordinary physical activity leads to fatigue, palpitation, dyspnea, or anginal pain; the person is comfortable at rest
- Class III: Marked limitation of physical activity in which less-than-ordinary activity results in fatigue, palpitation, dyspnea, or anginal pain; the person is comfortable at rest
- Class IV: Inability to carry on any physical activity without discomfort but also symptoms of heart failure or the anginal syndrome even at rest, with increased discomfort if any physical activity is undertaken

9.4.6 NT-proBNP

NT-proBNP measurements will be assessed by the central lab. NT-proBNP or BNP measurements for screening will be assessed locally.

9.4.7 Clinical outcome events

Potential pre-specified clinical outcome events will be submitted for adjudication to an independent CEC. The following events will be collected and analyzed to explore the efficacy of study drug treatments on clinical outcomes:

- All deaths (CV and non-CV, including outpatient death)
- CV hospitalizations including HF and non-HF hospitalizations and non-HF CV hospitalizations (i.e. myocardial infarction and stroke)
- Outpatient HF events, such as IV diuretic use for HF or urgent HF visits

The CEC will adjudicate all deaths as either CV or non-CV, and other events listed above in accordance with the pre-specified endpoint criteria in the adjudication charter. Investigators are mandated to report all suspected potential outcomes for adjudication by the CEC.

Events for adjudication should be reported as soon as critical data as defined in the eCRF page to the event adjudication is available. A query will be posted for events that require additional supporting documentation from the sites in order to render an adjudicated result and will be followed up by the sponsor. Every effort will be made to provide the CEC with clean eCRF data and required clinical data prior to event adjudication.

9.4.8 Six-minute walk test

The 6MWT is designed to evaluate a patient's exercise capacity while performing an everyday activity (32). During this study, a 6MWT including Borg CR 10 Scale will be conducted at different time points as specified in Section 9.2, for further details on assessment refer to Section 16.1. A familiarization 6MWT will be performed during the run-in phase. To avoid any interactions, it is not permitted to perform the familiarization test on the same day as the baseline 6MWT.

9.5 Pharmacokinetics / pharmacodynamics

For the investigation of systemic exposure to vericiguat and its relationship with efficacy, the plasma concentrations of vericiguat will be determined at different time points using a sparse sampling approach mainly in patients eligible for PK/QT assessment. EoT PK predose sample should be collected for all patients.

Blood samples will be collected at the time points indicated in Study Flow Chart in Section 9.1 and described in the visit description in Section 9.2. PK samples obtained at additional time points based on the investigator's discretion and/or from patients not eligible for PK/QT assessment will not qualify as a protocol deviation and will be analyzed. Deviations from the specified time points will be documented and taken into account. Date and time of the PK sample collection and date and time of last study drug intake (either at home on the day before the sample or at site) must be documented.

Details about the collection, processing, storage and shipment of samples will be provided separately (e.g. sample handling sheets or lab manual).

Plasma concentrations of vericiguat will be measured using validated methods. QC and calibration samples will be analyzed concurrently with study samples. Concentrations are calculated from the chromatographic raw data in accordance with current Bayer guidelines. The results of calibration samples and QC samples will be reported in the Bioanalytical

Reports which will be included in the Clinical Study Report for this study. The bioanalyst will be unblinded for analysis of study samples.

The PK calculations will be based on the actual sampling and dosing times. Therefore, it is of importance to have this data thoroughly documented in the eCRF. Deviations from the specified time points will be documented and taken into account when calculating the PK parameters. Those deviations do not qualify as protocol violations.

Pharmacokinetics and, if applicable, pharmacokinetics/pharmacodynamics (PK/PD) modeling using population approaches to describe vericiguat PK including potential influence of relevant patient co-variables (e.g., age, gender, body weight, etc.) or potentially to relate parameters of clinical safety and efficacy response (e.g. primary, secondary and/or exploratory variables) with vericiguat plasma concentrations will be investigated under a separate detailed PK/PD evaluation and analysis plan.

9.6 Safety

Safety and tolerability will be assessed by clinical review of all relevant parameters including:

Primary safety variable:

- The incidence of treatment-emergent AEs

Exploratory safety variables:

- Vital signs
- Laboratory data
- 12- lead ECG data

9.6.1 Adverse events

9.6.1.1 Definitions

Definition of adverse event (AE)

In a clinical study, an AE is any untoward medical occurrence (i.e. any unfavorable and unintended sign [including abnormal laboratory findings], symptom or disease) in a patient or clinical investigation patient after providing written informed consent for participation in the study. Therefore, an AE may or may not be temporally or causally associated with the use of a medicinal (investigational) product.

A surgical procedure that was planned prior to the start of the study by any physician treating the patient should not be recorded as an AE (however, the condition for which the surgery is required may be an AE).

In the following differentiation between medical history and AEs, the term “condition” may include abnormal e.g. physical examination findings, symptoms, diseases, laboratory, ECG.

- Conditions that started before signing of informed consent and for which no symptoms or treatment are present until signing of informed consent are recorded as medical history (e.g. seasonal allergy without acute complaints).
- Conditions that started before signing of informed consent and for which symptoms or treatment are present after signing of informed consent, at *unchanged intensity*, are recorded as medical history (e.g. allergic pollinosis).
- Conditions that started or deteriorated after signing of informed consent will be documented as adverse events. This includes intercurrent illnesses.

Definition of serious adverse event (SAE)

An SAE is classified as any untoward medical occurrence that, at any dose, meets any of the following criteria (a – f):

- a. Results in death
- b. Is life-threatening

The term ‘life-threatening’ in the definition refers to an event in which the patient was at risk of death at the time of the event, it does not refer to an event which hypothetically might have caused death if it were more severe.

- c. Requires inpatient hospitalization or prolongation of existing hospitalization

A hospitalization or prolongation of hospitalization will not be regarded as an SAE if at least one of the following exceptions is met:

- The admission results in a hospital stay of less than 12 hours
- The admission is pre-planned
(e.g. elective or scheduled surgery arranged prior to the start of the study; admission is part of the study procedures as described in Section 9.2)
- The admission is not associated with an AE
(e.g. social hospitalization for purposes of respite care).

However, it should be noted that invasive treatment during any hospitalization may fulfill the criterion of ‘medically important’ and as such may be reportable as an SAE dependent on clinical judgment. In addition, where local regulatory authorities specifically require a more stringent definition, the local regulation takes precedence.

- d. Results in persistent or significant disability / incapacity

Disability means a substantial disruption of a person’s ability to conduct normal life’s functions.

- e. Is a congenital anomaly / birth defect

- f. Is another serious or important medical event as judged by the investigator

9.6.1.2 Classifications for adverse event assessment

All AEs will be assessed and documented by the investigator according to the categories detailed below.

9.6.1.2.1 Seriousness

For each AE, the seriousness must be determined according to the criteria given in Section 9.6.1.1.

9.6.1.2.2 Intensity

The intensity of an AE is classified according to the following categories:

- Mild
- Moderate
- Severe

9.6.1.2.3 Causal relationship

The assessment of the causal relationship between an AE and the administration of treatment is a decision to be made by the investigator, who is a qualified physician, based on all information available at the time of the completion of the eCRF.

Causality should be assessed separately for each study treatment as detailed in the eCRF. If the investigator feels that the event cannot be firmly attributed to one of the study treatments (e.g. owing to a suspected underlying interaction), the same assessment will be documented for each study treatment.

The assessment is based on the question whether there was a “reasonable causal relationship” to the study treatment in question.

Possible answers are “yes” or “no”

An assessment of “no” would include:

1. The existence of a highly likely alternative explanation, e.g. mechanical bleeding at surgical site.
or
2. Non-plausibility, e.g. the patient is struck by an automobile when there is no indication that the drug caused disorientation that may have caused the event; cancer developing a few days after the first drug administration.

An assessment of “yes” indicates that the AE is reasonably associated with the use of the study treatment.

Important factors to be considered in assessing the relationship of the AE to study treatment include:

- The temporal sequence from drug administration: The event should occur after the drug is given. The length of time from drug exposure to event should be evaluated in the clinical context of the event.
- Recovery on drug discontinuation (de-challenge), recurrence on drug re-introduction (re-challenge): Patient’s response after de-challenge or re-challenge should be considered in view of the usual clinical course of the event in question.
- Underlying, concomitant, intercurrent diseases:
Each event should be evaluated in the context of the natural history and course of the disease being treated and any other disease the patient may have.
- Concomitant medication or treatment:
The other drugs the patient is taking or the treatment the patient receives should be examined to determine whether any of them might have caused the event in question.
- Known response pattern for this class of drug: Clinical/preclinical

- Exposure to physical and/or mental stresses: The exposure to stress might induce adverse changes in the recipient and provide a logical and better explanation for the event
- The pharmacology and pharmacokinetics of the study treatment: The pharmacokinetic properties (absorption, distribution, metabolism and excretion) of the study treatment, coupled with the individual patient's pharmacodynamics should be considered.
- The assessment is not possible

Causal relationship to protocol-required procedures

The assessment of a possible causal relationship between the AE and protocol-required procedure(s) is based on the question whether there was a “reasonable causal relationship” to protocol-required procedure(s).

Possible answers are “yes” or “no”

9.6.1.2.4 Action taken with study treatment

Any action on study treatment to resolve the AE is to be documented using the categories listed below.

- Drug withdrawn
- Drug interrupted
- Dose reduced
- Dose not changed
- Dose increased
- Not applicable
- Unknown

9.6.1.2.5 Other specific treatment(s) of adverse events

- None

9.6.1.2.6 Outcome

The outcome of the AE is to be documented as follows:

- Recovered/resolved
- Recovering/resolving
- Recovered/resolved with sequelae
- Not recovered/not resolved
- Fatal
- Unknown

9.6.1.3 Assessments and documentation of adverse events

The investigator has to record on the respective eCRF pages all adverse events occurring in the period between the signing of the informed consent and the end of the follow-up phase; after the end of the follow-up phase there is no requirement to actively collect AEs including deaths. The type of information that should be assessed and recorded by the investigator for each AE is listed in Section [9.6.1.2](#).

“Death” should not be recorded as an AE on the AE page. Instead, “death” is the outcome of underlying AE(s).

For all serious adverse events (SAEs) the sponsor has to carry out a separate assessment for expectedness, seriousness and causal relationship to study drug.

9.6.1.4 Reporting of serious adverse events

The definition of serious adverse events (SAEs) is given in Section [9.6.1.1](#). Each SAE must be followed up until resolution or stabilization by submission of updated reports to the designated recipient.

Investigator’s notification of the sponsor

All investigators will be thoroughly instructed and trained on all relevant aspects of the investigator’s reporting obligations for SAEs. This information, including all relevant contact details, is summarized in the investigator site file. This information will be updated as needed.

The investigator must report immediately (within 24 hours of the investigator’s awareness) all SAEs occurring during the observation period defined in Section [9.6.1.3](#) to the recipient detailed in the instructions for SAE reporting included in the Investigator File. For this, an AE page in the CRF as well as the complementary SAE pages provided in the CRF must be completed for each SAE.

SAEs occurring after the protocol-defined observation period will be processed by the sponsor according to all applicable regulations.

Notification of the IECs / IRBs

Notification of the IECs / IRBs about all relevant events (e.g. SAEs, suspected, unexpected, serious adverse reactions [SUSARs]) will be performed by the sponsor and/or by the investigator according to all applicable regulations.

In addition, adverse events related to study endpoints or underlined diseases may not be considered as SUSAR in this study (see Section [7.5](#)).

Notification of the authorities

The processing and reporting of all relevant events (e.g. SAEs, SUSARs) to the authorities will be done by the sponsor according to all applicable regulations.

Sponsor’s notification of the investigational site

The sponsor will inform all investigational sites about reported relevant events (e.g. SUSARs) according to all applicable regulations.

9.6.1.5 Expected adverse events

For this study, the applicable reference document is the most current version of the IB.

Overview listings of frequent events that have occurred so far in the clinical development are shown in the current IB. If relevant new safety information is identified, the information will be integrated into an update of the IB and distributed to all participating sites.

The expectedness of AEs will be determined by the sponsor according to the applicable reference document and according to all local regulations.

9.6.1.6 Adverse events of special safety interest

For this trial, the following safety related event of special interest has been defined:

- Symptomatic hypotension (all hypotension AEs will be captured, only symptomatic hypotension is considered an AESI)
- Syncope

The DMC will monitor with special attention to these AESIs as defined in the DMC charter.

Any of these events have to be reported as an “important medial event” (see Section [9.6.1.6](#)) and therefore as a SAE to the sponsor within 24 hours of becoming aware of the events.

In any case, adverse events of special interest fulfilling any seriousness criterion should be reported as SAE (see also Section [9.6.1.1](#)).

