### **6.3.2 Adverse events of special safety interest**

For this trial, the following adverse events are considered of special interest:

- Symptomatic hypotension events (Bayer SMQ "Hypotension (Riociguat)" (code=SMQ\_1388)). Hypotension events will be categorized in symptomatic/asymptomatic as captured in the eCRF.
- Syncope (Bayer SMQ "Syncope Riociguat"( code=SMQ\_1389))

For each of the SMQs, the following tables will be provided: overall summary of TEAEs, incidences of patients with TEAEs, and with serious TEAEs grouped by SOC and PT.

A listing of all hypotension and syncope events will be provided, including date, relative day (to study medication), dose group, preferred term and phase of the study (pre-treatment, during treatment, post-treatment).

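### Protocol 9.6.1.6 makes every symptomatic hypotension and syncope an SAE by event name, so the planned serious-TEAE tables largely stop grading these events and every arm's SAE incidence includes events serious only by this rule

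*Protocol*

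**What the plan says.** Protocol 9.6.1.6 names two AESIs, symptomatic hypotension and syncope. For hypotension it limits the scope: "all hypotension AEs will be captured, only symptomatic hypotension is considered an AESI". Any such event must be reported as an important medical event "and therefore as a SAE to the sponsor within 24 hours of becoming aware of the events". The cross-reference given there for an important medical event is Section 9.6.1.6, that is, the section itself. The next sentence reads: "In any case, adverse events of special interest fulfilling any seriousness criterion should be reported as SAE".

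Protocol 9.6.1.1 defines an SAE by criteria a to f. Criterion f is: "Is another serious or important medical event as judged by the investigator". Protocol 9.6.1.3 adds that for every SAE "the sponsor has to carry out a separate assessment for expectedness, seriousness and causal relationship to study drug".

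SAP 6.3.2 plans, for the hypotension SMQ and the syncope SMQ, an "overall summary of TEAEs, incidences of patients with TEAEs, and with serious TEAEs grouped by SOC and PT". It also states: "Hypotension events will be categorized in symptomatic/asymptomatic as captured in the eCRF". SAP 6.3.1 plans serious-TEAE incidence by treatment group and overall, with no separate handling of AESIs. Neither section says whose seriousness assessment is tabulated, and neither plans a table by seriousness criterion or by intensity.

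**The concern.** The reporting rule has one input, the name of the event. Hospital admission, threat to life, disability and case-level judgement do not enter. If the SAP tables use seriousness as reported, the serious column for syncope tends towards the any-event column, and the serious column for hypotension tends towards the symptomatic category that the SAP already records. The tables then give little by-arm information on how grave these events were.

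This matters because safety and tolerability is a primary objective. Protocol 3.3 also calls hypotension the main risk and says that hypotension and syncope at 15 mg still need characterising. Two kinds of misreading are possible. A rise in mild symptomatic events would appear as a rise in serious events. Conversely, if the total of symptomatic events were similar across arms but more of them led to admission in one arm, the SMQ tables would largely hide it.

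The wording is also open to uneven use. A site that follows the first sentence reports every AESI as serious. A site that follows the second may report only those that meet a criterion. The circular cross-reference does not settle which applies.

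**Working it through.** **Text.** Three statements bear on whether an AESI is serious.

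- 9.6.1.6, first sentence: always, by event name.
- 9.6.1.6, next sentence: when a seriousness criterion is fulfilled. This adds nothing if the first sentence already covers every AESI.
- 9.6.1.1, criterion f: an important medical event is a case-level judgement.

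Under the first sentence, P(serious | AESI) = 1 in every arm. Two groups keep a case-level assessment: asymptomatic hypotension inside the hypotension SMQ, and possibly SMQ terms that are not themselves an AESI (the SMQ contents are not given).

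**Size.** The documents give no SAE or AESI rate for this trial, so there is no stated figure to reproduce and what follows is illustration. Let

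- S = share of patients with an SAE when the name rule is not applied (assumed 10-30%, same in each arm);
- a = share of patients with an AESI;
- q = share of AESIs that would be serious anyway (assumed 10-50%).

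With AESIs independent of other SAEs, the rule adds (1 − S) × a × (1 − q) to an arm's SAE incidence. The artificial between-arm difference is (1 − S) × (a_drug − a_placebo) × (1 − q).

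The only pair of rates in the documents is in Protocol 3.3: 4.4% versus 3.3% hypotension AEs in the first 2 weeks at 2.5 mg in the earlier HFrEF study. These are all hypotension AEs, not AESIs, so using them as a is an assumption. With 245 per arm they give 245 × 0.044 = 10.8 and 245 × 0.033 = 8.1 patients, an excess of 2.7.

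- Vericiguat arm, added: from 0.7 × 0.044 × 0.5 = 1.5 points to 0.9 × 0.044 × 0.9 = 3.6 points.
- Placebo arm, added: from 0.7 × 0.033 × 0.5 = 1.2 points to 0.9 × 0.033 × 0.9 = 2.7 points.
- Difference: from 0.7 × 0.011 × 0.5 = 0.4 points to 0.9 × 0.011 × 0.9 = 0.9 points.

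Placebo therefore takes 3.3/4.4 = 75% of the inflation seen in a vericiguat arm.

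Other values of a, same ranges of S and q:

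| AESI rate, placebo / vericiguat | Added, placebo (points) | Added, vericiguat (points) | Artificial difference (points) |
|---|---|---|---|
| 3.3% / 4.4% (Protocol 3.3) | 1.2 to 2.7 | 1.5 to 3.6 | 0.4 to 0.9 |
| 5% / 5% (assumed) | 1.8 to 4.1 | 1.8 to 4.1 | 0 |
| 5% / 10% (assumed) | 1.8 to 4.1 | 3.5 to 8.1 | 1.8 to 4.1 |
| 5% / 15% (assumed) | 1.8 to 4.1 | 5.3 to 12.2 | 3.5 to 8.1 |

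**The case against.** A good deal can be said for the plan.

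- The rule works identically and under blinding in all three arms. A reader might infer that it inflates SAEs mainly on vericiguat. The documents do not support that: Protocol 3.3 reports similar hypotension AEs in all arms, placebo included, in the earlier HFpEF study, and Protocol 3.2.1 reports no blood pressure change at 10 mg against placebo. An excess at 15 mg is plausible but untested. This objection stands.
- A reader might also infer that the SAE difference is inflated several-fold. Under the formula above, the as-reported difference divided by the case-level difference is 1/q. That is 10 at q = 10% and 2 at q = 50%, so it only restates the assumed q and is not a finding about this trial. This stands too.
- It would be too strong to say the tables cannot show seriousness at all. Asymptomatic hypotension is still judged case by case, the sponsor assesses seriousness separately, results are shown by preferred term, TEAEs causing discontinuation are tabulated, and SAEs and deaths are listed. These help, but none is a planned by-arm comparison of how serious the AESIs were.
- The primary safety variable in Protocol 9.6 is TEAE incidence, which the rule leaves untouched. The SAE tables are descriptive, and no test uses them. This limits the consequence.
- Pre-specifying two events as medically important is a legitimate precaution, and the second sentence may be meant as a saving clause. That softens the conflict, but the overlap and the self-reference remain.

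**Conclusion.** The point holds as a reporting and tabulation weakness. Followed as written, and if the SAP uses reported seriousness, serious largely repeats symptomatic for hypotension and any event for syncope, and SAE incidence in every arm contains events that are serious only through 9.6.1.6. This part rests on the text and needs no assumed rate.

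The effect on the between-arm SAE difference depends on AESI rates that nobody yet knows. It is zero at equal rates and about 0.4 to 0.9 points with the HFrEF figures as stand-in. It becomes material only if an arm, most plausibly 15 mg, has clearly more AESIs than placebo. These sizes rest on the assumed ranges for S and q and on independence. The primary efficacy analysis and the primary safety variable are not affected. This is a cheap improvement, not a flaw that undermines the trial.

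**What to change.** Leave the 24-hour reporting of AESIs as it is. In SAP 6.3.1 and 6.3.2:

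- state whether the investigator's or the sponsor's seriousness assessment is tabulated;
- keep the as-reported serious-TEAE tables;
- add, by arm, a table of AESIs by seriousness criterion (at least one of a to e met; f only);
- show overall SAE incidence with and without AESIs that are serious solely through 9.6.1.6.

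The count based on criteria a to e should not replace the as-reported count. It would drop events an investigator independently judged important under f. It would also drop events whose only claim to seriousness is an admission of under 12 hours, which 9.6.1.1 excludes from criterion c. That could understate the drug's main risk.

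In Protocol 9.6.1.6, the two sentences must be reconciled with each other and with criterion f, and the self-referring cross-reference corrected.

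The cost is SAP wording, a few extra tables and a footnote explaining the two SAE counts. The proposal assumes that the SAE pages record which criterion was met and let events that are serious only by the name rule be told apart from those judged important under f. The documents do not confirm this.
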